3.1. Primary Objective

- To evaluate the preliminary safety and tolerability of CT-P59 up to Day 14 of the last enrolled patient.

3.2. Secondary Objectives

The secondary objectives are as follows:

- To evaluate the viral efficacy and characterization of SARS-CoV-2 viral isolates
- To evaluate the efficacy of CT-P59
- To evaluate the PK of CT-P59
- To evaluate additional safety of CT-P59 including immunogenicity

[figure not shown]
4. INVESTIGATIONAL PLAN

4.1. Study Design and Plan

This is a randomized, double-blind, placebo-controlled, parallel group, single ascending dose, Phase 1, pilot study to evaluate the safety, tolerability and virology of CT-P59 in combination with standard of care (SoC), except potential antiviral drugs and/or immune-based therapy under evaluation for treatment of SARS-CoV-2 infection, in patients with mild symptoms of SARS-CoV-2 infection. Approximately 18 patients in 3 cohorts are planned for enrollment and each cohort will consist of 6 patients, 5 of whom will receive CT-P59 and 1 of whom will receive a placebo. In each cohort, patients will be randomized in a 5:1 ratio to receive CT-P59 or placebo. This study will be started with the lowest dose that will maximize safety and the dose levels will be escalated to the higher doses.

The overview of the study is presented in [Figure 1](#).

Figure 1: Study Design Overview

After each study drug administration, patients will be observed for 48 hours for evaluation of the safety and tolerability of study drug.

When escalating dose from previous cohort to next cohort, Dose Escalation Committee (DEC) will review all available safety data of all patients in each cohort, within an observation period of 48 hours after study drug administration. If no safety or tolerability concern is observed, patients in next cohort will receive study drug. The dose escalation from a previous cohort to the next cohort will be stopped if one or more of the following stopping criteria are met:

- Two or more patients in one cohort experience treatment-emergent adverse event (TEAE)s of grade 3 or higher, which are considered to be related to study drug
- Four or more patients in one cohort experience TEAEs of grade 2 or higher, which are considered to be related to study drug
- One or more patients in one cohort experience a treatment-emergent serious adverse event (TESAE), which are considered to be related to study drug

If an event corresponding to the above criteria occurs within the observation period of 48 hours in each cohort and the dosing is temporarily stopped under the decision of DEC, the appointed independent Data and Safety Monitoring Board (DSMB) members will evaluate the relationship to CT-P59 of the event with unblinded manner and make a decision on continuation and the dose escalation of the study. If an event corresponding to the above criteria occurs after observation period of 48 hours in the previous cohort, further progression to next cohort will be temporarily stopped and the appointed independent DSMB members will review data and make a decision on continuation and the dose escalation of the study.

If it was revealed that an event corresponding to the above criteria occurs and all the TEAEs are related to CT-P59 as reviewed by DSMB members, the study will be temporarily stopped and the information will be submitted to regulatory authority for further evaluation and confirmation on continuation of the dose escalation of the study.

This study will comprise 4 study periods including Screening, Treatment Period, End-of-Treatment Visit and Follow-Up Period.

Screening (Day -7 to Day 1): Patients will sign and date the informed consent form (ICF) and undergo procedures to determine eligibility. During the Screening Period, retest for Screening is permitted only once by the Investigator's judgement. If the repeated test result is again not suitable or indeterminate for inclusion, the patient will be screen failed. Only one retest for reverse transcription polymerase chain reaction (RT-PCR) will be allowed, if study drug can be administered no more than 7 days from onset of symptom based on retest results. And, if there is available RT-PCR result confirming SARS-CoV-2 infection prior to obtaining written informed consent (but no more than 7 days from the onset of symptoms), the result can be allowed. If Screening visit date and the administration of study drug date (Day 1) are same, all assessments scheduled for the Screening and Day 1 visit can be performed only once on the date before randomization

Treatment Period (Day 1 to prior to End-of-Treatment Visit): Inclusion and exclusion criteria will be re-confirmed on Day 1. If it is concluded that the patients are not eligible in Day 1 assessments, the patient will be considered as Screening failure even if he/she was eligible based on assessments results performed during Screening Period. Patients will be randomized in 5:1 ratio to receive CT-P59 or placebo once all eligibility criteria have been confirmed. Patients will receive a single dose of CT-P59 or placebo on Day 1. All patients will be admitted to the study center on Day 1 and it is recommended to be confined up to Day 7. In-house stay period can be determined by Investigator considering the isolation regulation and/or public health capacity of the country, however all patients should be confined to the study center for at least 72 hours (until completion of all assessments on Day 3). After discharge, the consecutive study visits will be carried out on an out-patient basis. During the isolation period according to the local regulation, patients will visit the study center using the transportation provided by Sponsor.

End-of-Treatment Visit (Day 90): End-of-treatment (EOT) visit assessments will be performed on Day 90. If a patient is early terminated from the study, the patient will be asked to return to the study center as soon as possible for the safety assessments predefined for EOT visit.

Follow-Up Period (From End-of-Treatment Visit to Day 180): For all patients including a patient who early terminated from the study, each telephone call follow-up will occur bi-weekly from 2 weeks after the EOT visit to Day 180. During the Follow-Up Period, SARS-CoV-2 infection related signs and symptoms will be assessed by telephone call to capture the suspicious antibody dependent enhancement (ADE) occurrence. For patients with suspicious ADE occurrence, additional assessments will be conducted on unscheduled visit.

5. GENERAL STATISTICAL CONSIDERATIONS

Continuous data will be summarized using descriptive statistics: number of patients (n), mean, standard deviation (SD), minimum, median and maximum, unless otherwise specified. The descriptive statistics will be calculated using raw data before rounding although rounded values are listed. The following rules will be followed with regards to the number of decimal places:

- Minimum and maximum will be presented to the same number of decimal places in the source listing.
- Mean, median, geometric mean and percent coefficient of variation (CV%) will be rounded to one more decimal place than the maximum decimal place of values in the source listing.
- Standard deviation (SD) will be rounded to one more decimal place than mean.
- Only for PK section, point estimate and confidence intervals (CI) obtained from statistical procedures will be displayed to three decimal places. Also, standard error (SE) obtained from statistical procedures will be displayed to four decimal places.
- Kaplan-Meier estimates and days calculated using data/time will be displayed to two decimal places.

Geometric mean will not be reported if the dataset includes zero values and CV% will not be reported if the mean is zero.

Categorical data will be summarized using frequency tables showing numbers and percentages of patients. Percentages will be rounded to one decimal place and will be suppressed when the count is zero. The denominator for all percentages will be the number of patients within each treatment group for the set of interest, unless otherwise specified. Treatment group is defined in [Section 5.4](#).

Unscheduled visit will not be summarized in visit-based tables, unless otherwise specified. However, all data will be displayed in listings. Unless otherwise specified, listings will be sorted by the treatment group, patient number and visit, if applicable. In cases where more ordering is required, other variables will be included in the sort order as applicable.

When combining data from Electronic Case Report (eCRF) and analytical facilities such as Central Laboratory for PK, virology or immunogenicity, discrepancy will be handled as following:

- 1) Recorded as sample collected in eCRF but no corresponding results from analytical facility – listing will display only sample collection visit/date from eCRF;

- 2) No corresponding records in eCRF for results from analytical facility – listing will display only specimen collection visit/date and results from analytical facility;
- 3) Discrepancy in sample collection date from eCRF and analytical facility – listing will display results from analytical facility and visit/date from eCRF if not missing; if sample collection date is missing in eCRF then use specimen collection visit/date from analytical facility.

All available results from analytical facilities will be included in the summary table.

This SAP could be updated after the Data Review Meeting (DRM) but prior to database hard lock to document any deviations.

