## **2.2 Study Endpoints**

### **2.2.1 Primary Endpoints**

Primary endpoints will be analyzed based on the data up to Day 14 of the last enrolled patient.

- Treatment-emergent adverse events (TEAEs)
- Treatment-emergent serious AEs (TESAEs)
- Treatment-emergent AEs of special interest (TEAESI; infusion related reactions including hypersensitivity/anaphylactic reaction)
- Potential effects on the incidence of antibody-dependent enhancement (ADE)
- Vital signs (blood pressure, heart rate, body temperature, SpO2 and respiratory rate)
- Hypersensitivity monitoring
- Twelve-lead electrocardiogram (ECG)
- Severe Acute Respiratory Syndrome Coronavirus infection related signs and symptoms
- Radiography (chest x-ray and/or chest CT)
- Clinical laboratory test (clinical chemistry, hematology, and urinalysis)

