## **6.1.10 Radiography**

Radiography (chest x-ray and/or chest CT) will be performed at the scheduled time points specified in [Table 11-1](#) and when the Investigator considers it is clinically necessary (e.g., abnormal findings of SpO2).

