Some numeric parameters will be labeled with a CTCAE term, and grading will be applied to post-baseline values for numeric parameters where possible according to CTCAE version 5.0. Grades that require clinical input only will not be assigned to these parameters. Grades which are part numeric and part clinical input will be assigned based on the numeric portion only. If different grades share the same criteria due to exclusion of clinical input, lower grade will be used. The CTCAE terms and grades for applicable parameters are listed in [Appendix 4](#). The CTCAE grades for this analysis will be Grade 1 (Mild), Grade 2 (Moderate), Grade 3 (Severe) and Grade 4 (Life-threatening). The CTCAE Grade 5 (Death) will not be applied in this analysis since death cannot be determined from a numeric laboratory result. If the post-baseline result for a patient does not satisfy any CTCAE grade, it will be classified as “No Grade”.

Actual results and changes from baseline of numeric laboratory parameters including clinical chemistry, hematology, and urinalysis will be summarized using descriptive statistics by treatment group, parameter and scheduled visit in separate tables by laboratory category. For the purpose of summarization, any numeric values recorded from the clinical laboratory tests which are below the lower limit or above the upper limit of quantification will be set to the respective limit for all related summaries. In listings, original results containing inequality signs will be displayed.

The number and percentage of patients for clinical laboratory test results (clinical chemistry, hematology, and urinalysis) will be summarized using {“Normal”, “Abnormal, Not Clinically Significant”, “Abnormal, Clinically Significant”} categories as appropriate, by treatment group, parameter and visit, in the form of a shift table to detect changes from baseline, in separate tables by laboratory category.

The number and percentage of patients with a result for each CTCAE grade will be summarized by treatment group, laboratory category, CTCAE term and scheduled visit. Additional tables

will be generated using the most severe grade after study drug administration. The most severe grade will be selected including all post-baseline scheduled and unscheduled visits.

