12.5. Electrocardiogram

A 12-lead Electrocardiogram (ECG) will be performed at the time points specified in [Appendix 1](#) and [Appendix 2](#) and if the patient experienced cardiac symptoms during study drug administration. All scheduled 12-lead ECGs will be performed after the patient has rested quietly for at least 5 minutes. In case of hypersensitivity monitoring, any type of ECG can be performed. The findings of 12-lead ECG will be classified as either “Normal”, “Abnormal, Not Clinically Significant”, or “Abnormal, Clinically Significant”.

The number and percentage of patients will be summarized by treatment group, scheduled visit, in the form of a shift table to detect changes from baseline. All ECG data including hypersensitivity monitoring results will be listed for each patient by treatment group and visit.

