12.8. Radiography

Radiography (chest x-ray and/or chest CT) will be performed at the time points specified in

[Appendix 1](#). Results for radiography will be classified as either “Normal”, “Abnormal, Not Clinically Significant” or “Abnormal, Clinically Significant”.

The number and percentage of patients will be summarized by treatment group, scheduled visit, in the form of a shift table to detect changes from baseline. All radiography results will be listed by treatment group, visit.

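### The ECG and radiography shift tables count scheduled visits only, so event-driven films and ECGs at unscheduled visits are listed but not tabulated

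*SAP*

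**What the plan says.** Protocol 2.2.1 names 12-lead ECG and radiography among the primary endpoints, analysed on data up to Day 14 of the last enrolled patient.

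Both tests can also be done outside the schedule. Protocol 6.1.10 adds chest imaging "when the Investigator considers it is clinically necessary", with abnormal SpO2 as the example. SAP 12.5 adds ECGs to the scheduled ones: "and if the patient experienced cardiac symptoms during study drug administration". Protocol 6.1.5 allows any type of ECG for cardiac symptoms during hypersensitivity monitoring. Protocol Table 11-2 and SAP Appendix 2 call for ECGs at the suspicious-ADE visits, which both documents title as unscheduled.

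For analysis, SAP section 5 states: "Unscheduled visit will not be summarized in visit-based tables, unless otherwise specified". The next sentence reads: "However, all data will be displayed in listings". SAP 12.8 has radiography "summarized by treatment group, scheduled visit, in the form of a shift table to detect changes from baseline", and SAP 12.5 says the same for ECG. Neither section mentions unscheduled results in its table; both send all results to a listing. SAP 12.11 sends the suspicious-ADE evaluations to listings.

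For laboratory CTCAE grades, SAP 12.2 makes an explicit exception: "The most severe grade will be selected including all post-baseline scheduled and unscheduled visits".

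**The concern.** Under this rule, whether a result enters the table can depend on why the test was done. A routine Day 14 film is counted. A film taken between visits because the patient's oxygen saturation fell is not. The results that drop out of the by-group summary are the ones most likely to be abnormal.

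A patient whose prompted film shows a new abnormality that has cleared by Day 14 appears in the radiography table as unchanged. An ECG abnormality seen only at a suspicious-ADE visit appears in no ECG table. With groups of five and three, one such patient visibly alters the table.

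**Working it through.** The plan gives no figure to reproduce: the sample size rests on no hypothesis and the summaries are descriptive. The check is a reading of the general rule against the specific sections, a count of time points, and the weight of one patient.

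**1. Is there an exception to SAP section 5?**

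| Data | Table | Unscheduled results included? |
|---|---|---|
| ECG (SAP 12.5) | Shift table by scheduled visit | No exception stated |
| Radiography (SAP 12.8) | Shift table by scheduled visit | No exception stated |
| Laboratory clinical-significance categories (SAP 12.2) | Shift table by visit | No exception stated |
| Laboratory CTCAE worst grade (SAP 12.2) | Most severe post-baseline grade | Yes, explicitly |

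An unscheduled result taken before dosing can still count as baseline, because SAP 5.5 uses the last non-missing pre-dose value. The gap concerns post-dose results only.

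**2. Scheduled post-dose time points (SAP Appendix 1).**

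- Radiography: Day 14 only, so 1. Under the country-specific version, Days 3 and 14, so 2.
- ECG: Days 2, 7, 14, 28, 56 and 90, so 6, of which 3 fall by Day 14.

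**3. Which prompted tests are clearly excluded?** The section 5 rule speaks of unscheduled visits. Up to Day 14 the scheduled visit days are Days 1 to 7, 10 and 14, which is 7 + 1 + 1 = 9 days.

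- The other 14 − 9 = 5 days are Days 8, 9, 11, 12 and 13. A prompted test there is at an unscheduled visit and is excluded, except that Day 13 lies inside the ±1 day window of the Day 14 visit.
- Suspicious-ADE visits are unscheduled by their title, so their ECGs are excluded.
- A prompted film on Days 1 to 7 or 10 (other than Day 3 under the country-specific version) falls on a scheduled visit day on which no film was planned. The same holds for a prompted ECG after dosing on Day 1, or on Days 3 to 6 or 10. The SAP does not say whether these enter the table.

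**4. Weight of one patient.** Each cohort has 5 on CT-P59 and 1 on placebo. Pooled placebo over three cohorts is 3 × 1 = 3.

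- Dose group: 1/5 = 20.0 percentage points.
- Pooled placebo: 1/3 = 33.3 percentage points.

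As an illustration, suppose one of five patients in a dose group has an abnormal prompted film on Day 9 and a normal film on Day 14, and the other four have only normal films. The scheduled-visit table shows 0/5 = 0% abnormal at Day 14. A worst post-baseline row shows 1/5 = 20%.

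**The case against.** The case on the other side is substantial, and most of it limits the point.

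- **The results are reported.** A reader might infer that event-driven results are lost. They are not: SAP 5, 12.5, 12.8 and 12.11 list them all, and listings for 18 patients can be read in full.
- **Significant findings have another route.** A reader might infer that a clinically significant new infiltrate is tabulated nowhere. Protocol 6.1.1.1 makes a clinically significant abnormal diagnostic result an adverse event, and the TEAE tables in SAP 12.1.1 are not visit-based. A patient too ill for the Day 14 film can also appear in the oxygen, ICU, ventilation and hospitalisation tables of SAP 10.2. This stands, but the route is partial. Changes judged not clinically significant need not become adverse events. Protocol 6.1.13 leaves the reporting of infection-related signs and symptoms as adverse events to the investigator. An adverse event entry also leaves the shift table itself unchanged.
- **Not every prompted test is clearly excluded.** The SAP excludes unscheduled visits and is silent on an unplanned test on a scheduled day. That stands. An ECG during the infusion on Day 1 is in this unresolved group.
- **The Day 14 report has no such table.** A reader might infer that the primary Day 14 report understates abnormality through these tables. SAP Appendix 5 gives ECG and radiography as listings only in the first CSR, so the shift tables matter for the final CSR.
- **The laboratory precedent is narrower than it looks.** The laboratory shift table by clinical significance has no unscheduled exception either; only the CTCAE worst-grade table does. Protocol 7.4.3.4 itself specifies ECG shift tables at scheduled visits, so the SAP follows the protocol. A supplementary row contradicts neither document.
- **A worst-result row has its own bias.** It depends on how often each patient was tested, and it mixes x-ray with CT. That is a reason to label it and show it beside the scheduled-visit rows.

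**Conclusion.** The point holds in a limited form. Event-driven films and ECGs at unscheduled visits are not counted in the only tables planned for these two primary safety endpoints, and the handling of unplanned tests on scheduled days is undefined. The tables can therefore show no change for a patient with a transient abnormality. Each such patient is worth 20 percentage points in a dose group and 33 in pooled placebo, assuming the planned 5 and 3 patients are analysed. The documents give no expected frequency of prompted tests, so the number of patients affected cannot be estimated. The table shells are a separate addendum and could settle the unplanned-test question.

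The documents do not support a claim that the safety conclusion would change: the study is descriptive, everything is listed, and clinically significant findings should reach the TEAE tables. This is a gap in presentation that is worth closing.

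**What to change.** In SAP 12.5 and 12.8, keep the scheduled-visit rows and add a row or small companion table giving each patient's worst post-baseline result in the existing three categories. Use all scheduled and unscheduled post-dose results, once up to Day 14 and once up to end of treatment. Label it as including event-driven tests, and for radiography as combining x-ray and CT. State in the same place how a prompted test on a scheduled visit day is assigned when that test was not planned.

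The data are already collected, and SAP section 5 allows an update before hard lock. The cost is a few lines of SAP text and one extra row or table per endpoint in the final CSR. A Day 14 version in the first CSR would be a small new output, because Appendix 5 has no ECG or radiography table to extend. The price in interpretation is the dependence on testing frequency, which the labelling makes visible but does not remove.

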5.1. Software

All statistical analyses will be conducted using [REDACTED]

[REDACTED] PK parameters will be computed by [REDACTED]

5.2. Sample Size

The total sample size of 18 patients is not based on a formal statistical hypothesis. A sample size justification based on statistical hypothesis is not relevant in this study. The proposed number of 6 patients (5 patients for CT-P59 and 1 patient for placebo) in each cohort is set empirically based on sample sizes in other Phase 1 studies investigating the safety and tolerability of their study drugs and is considered to be sufficient to achieve the objective of the study.

5.3. Randomization, Stratification, and Blinding

On Day 1, eligible patients will be randomly assigned in 5:1 ratio to receive CT-P59 or placebo.

Patients who receive study drug and discontinue before the study completion will generally not be replaced. However, if a patient who receives study drug discontinues the study for a reason other than patient's safety, additional patient can be recruited upon decision of DEC. If a patient who randomized but did not receive study drug decides to discontinue the study, this patient can be replaced.

The randomization codes will not be revealed to study patients, investigator, and study center personnel except for delegated unblinded staff who will handle the study drug and predefined unblinded teams in the CELLTRION and [REDACTED] until all final data have been entered into the database and the database is locked and released for analysis.

Under normal circumstances, the blind should not be broken. The blind should only be broken if specific emergency treatment would be dictated as knowing the study drug assignment is required for medical management. In such cases, the investigator may, in emergency, determine the identity of the study drug by using the [REDACTED]

The date, time and reason for the unblinding must be documented in the source document and the appropriate field of the eCRF and the medical monitor will be informed as soon as possible.

All unblinding events will be reported to the medical monitor and CELLTRION. Any patients for whom the blind is broken may continue in the study at the investigator's discretion.

The overall randomization code will be broken only for reporting purposes. This will occur after database lock for data up to Day 14 of the last enrolled patient. The unblinded personnel will be predefined and documented before performing the analyses.

